5.2 Part B

[figure not shown]
Part B will be initiated after assessing safety, tolerability, PK, and PD data through Cohort 3 in Part A.

Multiple-ascending oral doses of LY3478045 will be administered once daily (QD) for 14 days in up to 4 cohorts. Each cohort will consist of 8 subjects. In Cohorts 1 and 3, six subjects will receive LY3478045 and 2 subjects will receive placebo. In Cohorts 2 and 4, six subjects will receive LY3478045 co-administered with a single dose of [CC1] and 2 subjects will receive placebo with a single dose of [CC1]. The maximum dose in males and females will be determined based on the PK analyses from previous cohorts.

A sentinel dosing strategy will be utilized in Cohorts 3 and 4, for which the mean AUC(0-24) is predicted to exceed [CC1] $\mu\text{g}\cdot\text{hr}/\text{mL}$. Two subjects (1 LY3478045 and 1 placebo) in the cohorts for which the mean AUC0-24 is predicted to exceed [CC1] $\mu\text{g}\cdot\text{hr}/\text{mL}$ will receive a sentinel dose on the same day. At least 48 hours after dose, the remaining subjects in each cohort may be dosed based on the available safety data.

Male subjects are allowed in Part B in the cohorts for which the predicted mean exposure AUC0-24 levels for the dose will not exceed [CC1] $\mu\text{g}\cdot\text{hr}/\text{mL}$, 1/10th exposure level observed at [CC1] mg/kg in dogs, which is the lowest dose tested in dogs with no testicular findings, as determined from PK data in Parts A and B.

Female subjects are allowed in Part B in every cohort. The predicted mean exposure AUC0-24 levels for the doses investigated in Part B will not exceed [CC1] $\mu\text{g}\cdot\text{hr}/\text{mL}$, 1/12th exposure level observed at [CC1] mg/kg in dogs, as determined from PK data in Parts A and B.

Abbreviations: AT = atorvastatin; LY = LY3478045; PL = placebo.

Figure GZKA.2 Illustration of study design for Part B

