9.3 Pharmacokinetic Assessment

The PK parameter estimates will be determined using non-compartmental methods in validated software program, Phoenix WinNonlin (Certara, Version 8.1 or later):

Pharmacokinetics of LY3470845

Following oral administration of LY3478045 (alone or with atorvastatin) in Part A and Part B, plasma concentrations of LY3478045 will be used to determine the following PK parameters where possible.

Parameter	Units	Definition
AUC(0-∞)	ng.h/mL	Area under the concentration versus time curve from time zero to infinity (Part A, Part B on Day 1 and 14 only)
AUC(0-t _{last})	ng.h/mL	Area under the concentration versus time curve from time zero to time t, where t is the last time point with a measurable concentration (Part A, Part B on Day 1 only)
AUC(0-6)	ng.h/mL	Area under the concentration versus time curve from time zero to 6h postdose
AUC(0-24)	ng.h/mL	Area under the concentration versus time curve from time zero to 24h postdose
AUC(6-12)	ng.h/mL	Area under the concentration versus time curve from time 6h to 12h postdose
AUC(12-24)	ng.h/mL	Area under the concentration versus time curve from time 12h to 24h postdose
AUC _T	ng.h/mL	Area under the concentration versus time curve during the dosing interval (Part B only)
%AUC(t _{last} -∞)	%	Percentage of AUC that is due to extrapolation from the last measurable concentration to infinity (Part A, Part B on Day 1 only)
C _{max}	ng/mL	Maximum observed drug concentration
t _{max}	h	Time of maximum observed drug concentration
t _{1/2}	h	Half-life associated with the terminal rate constant (λ_z) in non-compartmental analysis
CL/F	L/h	Apparent total body clearance of drug calculated after extra-vascular administration
V _{ss} /F	L	Apparent volume of distribution at steady state after extra-vascular administration (Part A only)
V _z /F	L	Apparent volume of distribution during the terminal phase after extra-vascular administration
RA(AUC)	NA	Accumulation ratio based upon AUC(0-24)

$$RA(AUC) = \frac{AUC(Day\ 14)}{AUC(Day\ 1)}$$

RA (C_{max}) NA Accumulation ratio based upon C_{max}

$$RA (C_{max}) = \frac{C_{max}(\text{Day 14})}{C_{max}(\text{Day 1})}$$

NA: Not applicable

In addition, dose normalised parameters will be calculated for AUC(0-∞), AUC(0-t_{last}), AUC(0-24) and C_{max} by dividing the calculated parameter by the dose of LY3478045.

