9.3.1 Pharmacokinetic Statistical Methodology

All PK parameters will be summarized using descriptive statistics.

PK dose proportionality will be assessed separately for Parts A and B (on Day 14 for Part B). Log-transformed C_{max} , AUC_{T} (Part B only), and $AUC(0-\infty)$ of LY3478045 will be evaluated using a power model (where log-dose acts as an explanatory variable) to estimate ratios of dose-normalized geometric means and corresponding 90% confidence intervals (CIs). The estimated ratio of dose-normalized geometric means of PK parameters between the highest and lowest doses will be used to assess dose proportionality. A subinterval within the highest and lowest doses may also be considered for assessment of dose proportionality using the same approach. The dose proportionality analysis for Part B will only be conducted if there are at least 3 different LY3478045 dose levels available for analysis.

Examples of the SAS code that will be used are as follows:

```
proc mixed data=xxxx;
model log_pk = log_dose / alpha=0.1 cl solution outpred=resids ddfm=kr;
estimate 'xx mg' intercept 1 log_dose yy / alpha=0.1 cl; /*Log value of xx*/
estimate 'zz mg - xx mg' log_dose pp / alpha=0.1 cl; /*Difference in log
values of zz and xx*/
ods output solutionf=est;
ods output estimates=estims;
run;
```

In Part B, the PK parameters, AUC_{T} , $AUC(0-\infty)$, and C_{max} , will be log-transformed prior to analysis. A linear mixed effects model will be fitted to the data. The model will include Subject as a random effect, and Day as a fixed effect. For each PK parameter, the difference in least-square treatment means (Day 14 – Day 1) along with the 90% CIs will be back-transformed to produce the ratio of geometric means and the CIs comparing Day 14 to Day 1.

Example of SAS code as follows:

```
proc mixed data=xxxx;
by treatment;
class day subject;
model log_pk = day /residual ddfm=kr;
random subject;
lsmeans day / cl pdiff alpha=0.1;
ods output lsmeans=lsm diffs=estims;
run;
```

To assess the effect that LY3478045 has on the primary **CCI** PK parameters, $AUC(0-\infty)$ and C_{max} , a linear fixed effect model on the parameters will be used. The response of the model will be the logged ratio of observations on Day 7 to Day-2. The model will include Treatment and the log of the baseline (Day -2) observation as fixed effects. For the Day 7 observations in Cohorts 2 and 4, the difference in least-square treatment means ([LY3478045 + **CCI**] –

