9.4.3 Fructose Tolerance Test

Fructose Tolerance Test (FTT): Three meals (breakfast, lunch, and dinner) will be served at approximately 20 minutes, 6 hours, and 12 hours after dose with low fructose content. A beverage containing mixture of fructose CCI CCI in approximately 300 to 500 mL of non-caloric solution) will be served with each of the

3 meals on Day 1 in Part A, and Days 1 and 14 in Part B. AUC(0-24), AUC(0-6), AUC(6-12), and AUC(12-24) for FTT will be calculated using trapezoid methods.

In Part A, the AUC(0-24), AUC(0-6), AUC(6-12), and AUC(12-24) from the FTT will be log-transformed prior to analysis. A linear fixed effects model will be fitted to the fructose data. The model will include Treatment as a fixed effect. The difference in least-square treatment means (LY3478045 – Placebo) along with the 90% CIs will be back-transformed to produce the ratio of geometric means and the CIs comparing LY3478045 to Placebo.

Example of SAS code as follows:

```
proc mixed data=xxx;
class treatment;
model log_AUC = treatment /residual ddfm=kr;
lsmeans treatment / cl pdiff alpha=0.1;
ods output lsmeans=lsm diff=estims;
run;
```

In Part B, the AUC(0-24), AUC(0-6), AUC(6-12), and AUC(12-24) from the FTT will be log-transformed prior to analysis. A linear mixed effects model will be fitted to the data. The model will include treatment, day and the interaction between treatment and day as fixed effects and subject as a random effect. The difference in least-square treatment means (LY3478045 – Placebo) along with the 90% CIs will be back-transformed to produce the ratio of geometric means and the CIs comparing LY3478045 to Placebo. Similar comparisons will be calculated between Day 14 and Day 1 for LY3478045.

Example of SAS code as follows:

```
proc mixed data=xxx;
class treatment day subject;
model log_AUC = treatment|day /residual ddfm=kr;
random subject;
lsmeans treatment*day / cl pdiff alpha=0.1;
ods output lsmeans=lsm diff=estims;
run;
```

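### The Part B comparison of AUC(0-∞) on Day 14 with Day 1 carries over drug from 13 earlier doses, so it is not 1 when clearance is unchanged and cannot show a change in clearance

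*SAP*

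**What the plan says.** SAP Section 9.3.1 log-transforms three LY3478045 parameters in Part B (AUCτ, AUC(0-∞) and Cmax) and compares each on Day 14 with the same parameter on Day 1. On the model it says "The model will include Subject as a random effect, and Day as a fixed effect". The difference in means, with its interval, "will be back-transformed to produce the ratio of geometric means and the CIs comparing Day 14 to Day 1". The example code has "lsmeans day / cl pdiff alpha=0.1", so the intervals are 90%. The code also fits each treatment separately through a BY statement, which the text does not mention.

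The parameter table in SAP Section 9.3 confirms that AUC(0-∞) is derived on both days: "Area under the concentration versus time curve from time zero to infinity (Part A, Part B on Day 1 and 14 only". The same table defines RA(AUC) and RA(Cmax) as the Day 14/Day 1 ratios of AUC(0-24) and Cmax. It also lists CL/F, which is summarised descriptively and is not the outcome of any model.

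On dosing, SAP Section 5.2 says "Multiple-ascending oral doses of LY3478045 will be administered once daily (QD) for 14 days in up to 4 cohorts". Thirteen doses therefore precede the Day 14 dose.

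**The concern.** AUC(0-∞) is a clearance measure after a single dose, because it then equals bioavailable dose over clearance. After the fourteenth daily dose, the area from that dose to infinity also contains everything still in the body from doses 1 to 13. The Day 14/Day 1 ratio of AUC(0-∞) therefore has no fixed reference value. It exceeds 1 when nothing has changed, by an amount that depends on the half-life.

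The contrast that does have a reference value is AUCτ at steady state over AUC(0-∞) after the first dose. Under linear, time-invariant kinetics it equals 1. No planned model contains it.

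Describing single- and multiple-dose PK is the secondary objective, with AUC(0-∞) a named endpoint (Protocol Section 4). The PK data are also meant to help identify a dose range for later studies (Protocol Section 3.1). An AUC(0-∞) ratio above 1 could be read as falling clearance. A real rise in clearance could be offset by carry-over and go unseen.

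**Working it through.** The plan states no power, precision or expected ratio for this analysis, so there is no figure to reproduce.

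**Inputs.** From the documents: dosing interval τ = 24 h and N = 14 doses (SAP Section 5.2); Part B Day 1 sampling to the 24 h predose sample (Protocol Sections 2.2 and 2.3). Assumed: half-lives of 4 to 24 h, absorption rate ka = 1/h, one compartment.

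**Step 1: carry-over with constant clearance.** Scale the single-dose curve so that Day 1 AUC(0-∞) = 1. With c = 1/(1/k − 1/ka) and R(λ) = (1 − e^(−Nλτ))/(1 − e^(−λτ)):

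- Day 14 AUC(0-∞) = c·[R(k)/k − R(ka)/ka]
- Day n AUCτ = c·[(1 − e^(−nkτ))/k − (1 − e^(−n·ka·τ))/ka]

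Example at 12 h: k = 0.0578, 1/k = 17.31, R(k) = 1.333, R(ka) = 1.000. Day 14 AUC(0-∞) = (1.333 × 17.31 − 1)/(17.31 − 1) = 1.35.

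| Assumed half-life | Planned AUC(0-∞) ratio, Day 14/Day 1 | AUCτ ratio, Day 14/Day 1 | AUCτ(Day 14)/AUC(0-∞)(Day 1) | Day 1 AUC(0-∞) beyond 24 h |
|---|---|---|---|---|
| 4 h | 1.02 | 1.02 | 1.00 | 1.9% |
| 6 h | 1.08 | 1.08 | 1.00 | 7.1% |
| 12 h | 1.35 | 1.36 | 1.00 | 26.5% |
| 24 h | 2.03 | 2.06 | 1.00 | 51.5% |

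**Step 2: a real change in clearance.** Let clearance change from the second dose on, with volume constant.

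| Half-life | Clearance | Planned AUC(0-∞) ratio | AUCτ(Day 14)/AUC(0-∞)(Day 1) |
|---|---|---|---|
| 12 h | ×1.25 | 0.99 | 0.80 |
| 24 h | ×1.25 | 1.40 | 0.80 |
| 24 h | ×1.5 | 1.05 | 0.67 |

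The planned ratio can look like no change, or like plain accumulation, while clearance has risen by 25% or 50%.

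**Step 3: decline that is not mono-exponential.** With half of the AUC at a 4 h half-life and half at 48 h, and clearance constant, the planned ratio is 2.22 and the AUCτ ratio 1.58. They differ, and neither is 1.

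**Step 4: the replacement as it would be estimated.** Take noise-free bi-exponential profiles with constant clearance and true Day 1 AUC(0-∞) = 1. Apply the scheduled Day 1 times and the SAP's linear-log rule, and fit the terminal slope to the 12, 16 and 24 h points.

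| Half-lives (share of AUC) | Estimated Day 1 AUC(0-∞) | AUCτ(Day 14) over that estimate | Apparent extrapolation | Estimated half-life |
|---|---|---|---|---|
| 4/48 h (50:50) | 0.707 | 0.996/0.707 = 1.41 | 11% | 8.2 h |
| 4/24 h (50:50) | 0.843 | 1.000/0.843 = 1.19 | 14% | 8.8 h |
| 6/36 h (70:30) | 0.858 | 0.9995/0.858 = 1.16 | 12% | 7.8 h |

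The slow phase is missed, so the ratio exceeds 1 with clearance unchanged. In these three cases the apparent extrapolation stays below the SAP's 20% flag. The 12 h fitting window, however, covers only 12/8.2 = 1.5, 12/8.8 = 1.4 and 12/7.8 = 1.5 half-lives. That is under the 2 half-lives at which the SAP flags a half-life estimate.

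**The case against.** The strongest objection is to the replacement. Its true value is 1, but the estimate rests on a Day 1 profile cut at 24 h. For mono-exponential decline, more than a quarter of the Day 1 area is extrapolated at a 12 h half-life and about half at 24 h. With a slow terminal phase, the estimate can itself suggest a fall in clearance that did not occur. This stands and limits how the result may be read. It does not rescue the planned contrast, which uses the same Day 1 AUC(0-∞) and adds carry-over to it.

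Second, the objective is to determine the PK, not to test time-invariance; CL/F is derived and summarised, and RA(AUC) sits beside the modelled ratios. This is fair. A reader might infer that the plan ignores clearance; it does not. It lacks a paired contrast with an interval, and the SAP does not say which AUC is the denominator of CL/F on each day.

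Third, a reader might infer that the AUC(0-∞) ratio merely repeats the accumulation ratio. That is nearly so for mono-exponential decline, but not in general (2.22 against 1.58 in Step 3).

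Fourth, a reader might infer that fitting by treatment, with six active subjects and 5 residual degrees of freedom per dose, is an error because SAP Section 9.4.3 uses one treatment-by-day model. The documents do not support that. The fructose analysis must compare with placebo, whereas this contrast is within subject and within dose. Pooling assumes a common within-subject variance across ascending doses, and its 20 degrees of freedom need all four cohorts, where the plan says up to four.

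**Conclusion.** The point holds for the AUC(0-∞) contrast alone. With clearance constant, the planned ratio is about 1.02, 1.08, 1.35 and 2.03 at half-lives of 4, 6, 12 and 24 h, so it has no reference value of 1 and does not test for a change in clearance. These sizes rest on an assumed one-compartment model with ka = 1/h and on assumed half-lives. At about 4 h or less the matter is trivial; at 12 h or more the ratio can mislead. The AUCτ and Cmax contrasts are sound measures of accumulation.

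**What to change.** In SAP Section 9.3.1:

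- Keep the Day 14/Day 1 contrasts of AUCτ and Cmax, labelled as accumulation.
- Replace the AUC(0-∞) contrast with log AUCτ(Day 14) minus log AUC(0-∞)(Day 1), back-transformed with a 90% CI and read against 1.
- Show the 20% extrapolation flag beside it, repeat it without flagged subjects, and do not read it as a clearance change when most Day 1 values are flagged.
- Because the 20% flag misses the bi-exponential cases in Step 4, also show the SAP's half-life flag and set the Day 1 half-life beside the Day 14 half-life, which is sampled to 72 h. A clearly longer Day 14 half-life warns that the Day 1 area may be too small.
- State the AUC used for CL/F on each day.
- Make the text and the BY-treatment code agree. One joint treatment-by-day model is optional and not part of this point.

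The cost is SAP wording and code, with no new samples or subjects. The remaining downside is that the new contrast is weakest at long half-lives, where carry-over is largest, and dropping flagged subjects from six per dose may leave few.

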9.4 Pharmacodynamic Assessment

9.4.1 CCI █

Plasma concentrations of CCI █ will be listed and summarized by part and treatment, using standard descriptive statistics. Parameters, including predose observed drug concentration ($C_{predose}$), C_{max} , t_{max} , $AUC(0-t_{last})$, and $AUC(0-24)$, will be summarized using descriptive statistics.

In addition, a comparison between log-transformed $C_{predose}$ and C_{max} of CCI █ will be produced using a linear mixed effects model with treatment, concentration phase, and subject as a random effect, where the variable concentration phase will be a variable which indicates whether the concentration value is predose ($C_{predose}$) or postdose (C_{max}). The difference between postdose and predose will be calculated for each treatment and will be back-transformed to present the ratios of geometric least squares means and the corresponding 95% CIs.

The following comparisons will be calculated from the model (including associated p-values):

- Postdose versus predose for each treatment group and placebo
- At the postdose timepoint, comparisons between each treatment group and placebo

For Part A, the data will be those samples collected from the Day 1 timepoint. For the Part B analysis, an additional fixed effect for day will be added to the model so that comparisons can be performed for each day. For all cohorts in Part B, the data collected from the Day 1 and Day 7 samples will be used. This will be a repeated measures model with an unstructured covariance structure and a compound symmetric structure will be used if the model fails to converge.

Example SAS code for the analysis (Part A):

```
proc mixed data=xxxx;
  class trtmnt concphase subject;
  model conc = trtmnt concphase / ddfm=kr;
  random subject;
  lsmeans trtmnt / pdiff cl alpha=0.05;
  lsmeans concphase / pdiff cl alpha=0.05;
  ods output lsmeans=lsmeans diffs=diffs;
```

run;

Example SAS code for the analysis (Part B):

```
proc mixed data=xxxx;
class treatment day subject;
model logpk = treatment day treatment*day /residual ddfm=kr;
repeated day / subject=subject type=UN;
lsmeans treatment*day / cl pdiff alpha=0.05;
ods output lsmeans=lsm diffs=estims;
run;
```

Plasma concentrations of CCI will also be plotted against dose. The plot will be produced separately by dose level and repeated to include all dose levels on one plot.

Additional analysis may be performed, if warranted, upon review of the data.

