2.1. Part A (Single-Ascending Doses)

	Screening	Days							FU ^a	ED ^b	Comments
Procedure	^c ≤28 days before Day -1	-1	1	2	3	4	5	7	14		
Informed Consent	X										
Admission to CRU		X									
Discharge from CRU						X					Subjects may be discharged on Day 5 at the discretion of the investigator.
Non-Residential Visit							X	X	X	X	
LY3478045 Administration			X								
Medical History	X										Information regarding occasional use of vitamin/mineral supplements will be taken as a part of the medical history evaluation at the time of subject screening.
Complete Physical Examination	X								X	X	Targeted PE may be conducted at other visits at the discretion of the investigator.
Height	X										
Weight	X	X									
Pregnancy Test	X	X							X	X	Serum pregnancy test will be performed at screening and urine pregnancy test will be performed at all other specified timepoints.
Blood Pressure and Pulse Rate (Supine) ^c	X	X	P, every 1 h up to 12 h postdose	24, 36 h	48 h	72 h		X	X	X	
Body Temperature	X	X							X	X	
Clinical Laboratory Tests	X	X	P	X	X			X	X		See Appendix 2 for complete list.
Serum Creatinine ^d			P, 4, 12, 24 h								
TriPLICATE 12-Lead ECG			Predose: 1.5 h, 1 h, and 30 min. Postdose: 0.5, 1.5, 2.5, 4, 6, 8,	24 h							

	Screening	Days							FU ^a	ED ^b	Comments
Procedure	≤28 days before Day -1	-1	1	2	3	4	5	7	14		
			10, 12, 16 h								
Single 12-Lead ECG	X				X				X	X	
Adverse Event Recording	X	X	X	X	X	X	X	X	X	X	
Pharmacokinetic Sampling ^d			P, 0.75, 1.5, 3, 4, 6, 8, 10, 12, 16 h	24 h	48 h	72 h	96 h				
Meal (Low Fructose)			20 min, 6, 12 h								
Fructose Beverage (for Fructose Tolerance Test)			during meal: 20 min, 6, 12 h								
Fructose Tolerance Test Assay ^d			CCI	CCI							
Genetic Sample			X								
Fasting Biomarker Samples (Nonpharmacogenetic)		X		X							
CCI			P, 0.75, 1.5, 3, 4, 8, 12, 16 h	24 h	48 h	72 h	96 h				
24-hour Urine Collection for LY3478045 and Creatinine ^d			0-12, 12-24 h	24-36, 36-48 h	48-60, 60-72 h						

Abbreviations: CRU = clinical research unit; ECG = electrocardiogram; ED = early discontinuation; FU = follow-up; h = hour(s); min = minutes; P = predose; PE = physical examination.

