9.8.1.1. Bioanalysis

Samples will be analyzed at a laboratory approved by the sponsor and stored at a facility designated by the sponsor.

CCI will be assayed using a validated liquid chromatography tandem mass spectrometry method. It is planned that samples collected from both LY3478045- and placebo-treated subjects will be analyzed.

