AUC(0-t _{last})	ng.h/mL	Area under the concentration versus time curve from time zero to time t, where t is the last time point with a measurable concentration
AUC(0-24)	ng.h/mL	Area under the concentration versus time curve from time zero to 24 hours postdose
C _{max}	ng/mL	Maximum observed drug concentration
C _{predose}	ng/mL	Predose observed drug concentration
t _{max}	h	Time of maximum observed drug concentration

Additional PK parameters may be calculated where appropriate.

The software and version used for the final analysis will be specified in the clinical study report. Any exceptions or special handling of data will be clearly documented within the final study report.

Plasma PK analysis will, where possible, be carried out using actual postdose times recorded in the raw data.

Interim plasma PK analysis will be performed by Lilly for the decision regarding dose escalation.

Urine PK analysis will be calculated using nominal sample collection times

Formatting of tables, figures and abbreviations will follow the Eli Lilly Global PK/PD/TS Tool: NON-COMPARTMENTAL PHARMACOKINETIC STYLE GUIDE. The version of the tool effective at the time of PK analysis will be followed.

General PK Parameter Rules

- Actual sampling times will be used in the final analyses of individual PK parameters, except for non-bolus pre-dose sampling times which will be set to zero.
- C_{\max} and t_{\max} will be reported from observed values. If C_{\max} occurs at more than one time point, t_{\max} will be assigned to the first occurrence of C_{\max} .
- AUC parameters will be calculated using a combination of the linear and logarithmic trapezoidal methods (linear-log trapezoidal rule). The linear trapezoidal method will be applied up to t_{\max} and then the logarithmic trapezoidal method will be used after t_{\max} . The minimum requirement for the calculation of AUC will be the inclusion of at least three consecutive plasma concentrations above the lower limit of quantification (LLOQ), with at least one of these concentrations following C_{\max} .
- AUC($0-\infty$) values where the percentage of the total area extrapolated is more than 20% will be flagged. Any AUC($0-\infty$) value excluded from summary statistics will be noted in the footnote of the summary table. If AUC($0-\infty$) cannot be determined for all subjects an alternative AUC measure, such as AUC to a fixed time point, may be used in the assessment exposure between dose groups and metabolite ratios.

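### The within-group Cmax/Cpredose test in SAP 9.4.1 sets the highest of 7 (or 8) postdose samples against one predose sample, so its no-effect value is above 1 and its p-value cannot be read

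*SAP*

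**What the plan says.** SAP Section 9.4.1 fits a mixed model to the log concentrations of a redacted biomarker. A phase variable marks each value as predose (Cpredose) or postdose (Cmax). By the general rules in SAP Section 9.3, Cmax values "will be reported from observed values", so Cmax is the highest measured sample.

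Section 9.4.1 then states: "The difference between postdose and predose will be calculated for each treatment and will be back-transformed". The results are presented as "ratios of geometric least squares means and the corresponding 95% CIs". Two sets of comparisons are listed, both with p-values:

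- "Postdose versus predose for each treatment group and placebo";
- each treatment group against placebo at the postdose timepoint.

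Part A uses the Day 1 samples and Part B uses Days 1 and 7. The Part A example code has treatment and phase as main effects without their interaction. The Part B example code has treatment, day and their interaction, but no phase term.

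In Protocol Section 2.1, the Day 1 column of the redacted biomarker row reads "P, 0.75, 1.5, 3, 4, 8, 12, 16 h", followed by single samples at 24, 48, 72 and 96 h. Protocol Section 9.8.1.1 states: "It is planned that samples collected from both LY3478045- and placebo-treated subjects will be analyzed".

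**The concern.** The first listed comparison sets a selected maximum against one unselected value from the same fluctuating series. If the analyte is present without drug and simply varies from sample to sample, the maximum will usually be the larger. The ratio of geometric means then has a no-effect value above 1, while the interval and p-value are computed as if it were 1.

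At stake is a set of p-values that would usually point to a rise in the biomarker at most dose levels when nothing has happened. They would be printed beside a placebo comparison that is sound. The study is first-in-human and is meant to inform later trials, so an uninterpretable p-value should not be offered as inference, even for an exploratory measure.

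**Working it through.** The plan gives no variance, power or error rate for this analysis, so there is no figure of its own to reproduce.

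**Inputs from the documents**

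- Samples per profile (Protocol Sections 2.1 to 2.3): 1 predose and 7 postdose on the dosing day in both Parts, or 8 with the 24 h sample.
- Check against Protocol Appendix 5: Part A 1 + 7 + 4 = 12; Part B Cohorts 1 and 3, 2 × 9 = 18; Cohorts 2 and 4, 3 × 9 = 27. These equal the redacted 3 mL rows (12, 18, 27). This supports tying the schedule row to Section 9.4.1, but the tie remains an inference.
- Group sizes (SAP Section 5): 6 active and 2 placebo per cohort. Pooled Part A placebo is 10 (five cohorts) or 8 (four). Part B has two placebo treatments of 4 each, or 8 if pooled.
- Level: two-sided 5%, from the 95% CI.

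**Assumptions**

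Log concentrations are Gaussian, with no drug effect and no time-of-day or meal trend. Within-subject SD is σ. Noise is either independent or serially correlated with a half-life of 2 to 24 h.

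**Hand calculation, independent noise, 7 samples**

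For each subject, d = log Cmax − log Cpredose; the subject's own level drops out.

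- Mean of d = σ × (expected maximum of 7 standard normals) = 1.352σ.
- SD of d = σ√(1 + 0.392) = 1.180σ, where 0.392 is the variance of that maximum.
- Spurious ratio = exp(1.352σ), with σ = √ln(1 + CV²). At an assumed CV of 10%, 20% or 30%, the ratio is 1.14, 1.31 or 1.49.
- Active group, n = 6: 1.352 / (1.180/√6) = 1.352/0.482 = 2.81. Five Part A cohorts leave 40 − 6 = 34 residual degrees of freedom, with critical t 2.03. The chance of a significant rise is 78%.
- Pooled placebo, n = 10: 1.352 / (1.180/√10) = 3.62, giving 94%.
- Part A code as written, one phase effect over 40 subjects: 1.352 / (1.180/√40) = 7.25, giving about 100%.

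σ cancels from the test statistics, so these rates do not depend on the assumed CV. Only the size of the ratio does.

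**Simulation, 7 samples, pooled residual variance: chance of a significant rise with no drug effect**

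| Contrast | Independent noise | Half-life 24 h |
|---|---|---|
| Part A active, n = 6 | 78% | 63% |
| Part A placebo, n = 10 | 94% | 87% |
| Part A placebo, n = 8 | 88% | 77% |
| Part B active, n = 6 | 77% | 57% |
| Part B placebo pooled, n = 8 | 88% | 71% |
| Part B placebo separate, n = 4 | 60% | 41% |
| All Part A groups at once (five cohorts) | 29% | 8% |
| All Part A groups at once (four cohorts) | 34% | 11% |

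Shorter half-lives lie between the two columns or a point or so above the left one. With 8 samples the active-group rates run from 65% to about 85%. If the software lets the predose sample count towards Cmax, the active-group rate is 90% (7 postdose samples, independent noise).

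**Placebo-referenced contrasts under the same conditions**

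- Cmax on active against Cmax on placebo: 4.7% to 5.3%.
- Change on active minus change on placebo: 4.6% to 5.3%.
- Cmax against placebo with predose as a covariate: about 5%.

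All groups within a Part share the same sampling times, so the selection effect is on both sides and cancels.

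**Day 7 in Part B**

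Dosing is daily from Day 1, so the Day 7 predose sample follows six doses. If the drug has multiplied the level by k throughout the day, then Cmax/Cpredose = (k × Cmax)/(k × Cpredose). The factor k cancels, and a sustained effect would be missed even after placebo correction.

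**The case against.** The strongest reply is that a valid test is already planned. The second comparison sets Cmax on each dose against Cmax on placebo, compares maximum with maximum, and keeps its 5% level. The placebo post/pre ratio is also shown, so a careful reader would see placebo rise too. The analysis is exploratory and no decision rule hangs on it. All of this stands, and it confines the point to the first comparison. It does not rescue that comparison, which still carries p-values against a wrong null. The second comparison, as planned, also makes no use of the subject's own predose value.

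The size rests on assumptions. Part A Day 1 and Part B Days 1 and 14 include three meals with a fructose beverage. A falling within-day trend would shrink the artefact and a rising one would enlarge it. Either way, 1 would not be a safe null value without a placebo reference.

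A reader might infer two stronger things that the documents do not support:

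- **That every group will show a significant rise.** With the per-treatment contrasts in the SAP text, all Part A groups are significant together in only about 8% to 34% of null trials. Near-certainty belongs to the additive Part A code alone.
- **That Part A uses 11 postdose samples and is therefore not comparable with Part B.** Section 9.4.1 restricts Part A to Day 1, where there are 7, as in Part B. It plans no comparison between Parts.

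Finally, neither code block fits the per-treatment post/pre contrasts that the text describes. The rates for those contrasts therefore follow the text, not the code.

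**Conclusion.** The point holds for the within-group comparison only. Its no-effect ratio is above 1: about 1.14 to 1.49 for 7 independent samples at an assumed CV of 10% to 30%, and less with serial correlation. With no drug effect it is falsely significant in roughly 60% to 80% of active groups (57% to 79% over the settings examined with 7 samples). For pooled placebo the figure is 71% to 95%; for separate Part B placebo groups of 4 it is lower, at 41% to 60%. Under the Part A code, one shared ratio is significant almost always. These figures assume no time trend and that the redacted schedule row is the analyte of Section 9.4.1.

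The analysis is exploratory, so this is a correction that should be made, not a threat to the study's primary conclusions.

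**What to change.** Amend SAP Section 9.4.1 as follows.

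1. Report the within-group Cmax/Cpredose ratio descriptively, for active and placebo, without a p-value or a test against 1.
2. On Day 1 (Parts A and B), base inference on log Cmax for each dose against placebo, with the subject's Day 1 predose value as covariate. The placebo-corrected Cmax/Cpredose ratio is an acceptable alternative on this day.
3. On Day 7 (Part B), compare log Cmax with placebo, adjusted for the Day 1 predose value, which precedes any LY3478045. Do not use the Day 7 predose value.
4. Re-specify both code blocks to match. If the ratio form is kept, Part A needs a treatment-by-phase term; without one, the placebo-corrected contrast is identically zero. Part B needs a phase term with its interactions. An added ESTIMATE statement alone is not enough.
5. State whether the two Part B placebo treatments are pooled. On Day 7, Cohorts 2 and 4 receive atorvastatin and Cohorts 1 and 3 do not.
6. State whether the 24 h sample, and the predose sample itself, can count towards Cmax.

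The cost is SAP text and model code, with no new samples. The downside is precision. With a common residual SD s, the standard error of a within-group change is s√(1/6). The placebo-corrected one is s√(1/6 + 1/10), wider by √1.6 = 1.26. With 8 placebo subjects the factor is √1.75 = 1.32, and with 4 it is √2.5 = 1.58.
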